1.3.2 Part B

Procedure	Intervention period (Part B)																		Safety Follow-up ^b	Early discontinuation visit																				
	Day 350 ± 7	Week 50	Day 364 ± 7 ^a	Week 52	Day 378 ± 7	Week 54	Day 392 ± 7	Week 56	Day 406 ± 7	Week 58	Day 420 ± 7	Week 60	Day 434 ± 7	Week 62	Day 448 ± 7	Week 64	Day 462 ± 7	Week 66	Day 476 ± 7	Week 68	Day 490 ± 7	Week 70	Day 504 ± 7	Week 72	Day 532 ± 7	Week 76	Day 560 ± 7	Week 80	Day 588 ± 7	Week 84	Day 616 ± 7	Week 88	Day 644 ± 7	Week 92	Day 672 ± 7/ EOT	Week 96 / EOT				
Visit	21	22	23	24	25	26	27	28	29	30	31	32	33	34	35	36	37	38	39																					
Concomitant therapy and procedures recording																																					X			
IRT contact																																					X			
IMP dispensation/reconciliation ^c																																					X ^d			X ^d
Safety																																								
Physical examination ^e			X																																		X	X	X	
Neurological examination ^f			X																																		X	X	X	
Weight			X																																		X	X	X	
Vital signs ^g			X																																		X	X	X	
12-lead ECG			X																																		X	X	X	
Laboratory tests for hematology and chemistry	X ^h	X	X ^h	X ^h	X ^h	X ^h	X ^h	X ^h	X ^h	X ^h	X ^h	X ^h	X ^h	X ^h	X ^h	X ^h	X ^h	X ^h	X ^h	X ^h	X ^h	X ^h	X ^h	X ^h	X ^h	X ^h	X ^h	X ^h	X ^h	X ^h	X ^h	X ^h	X ^h	X ^h	X ^h	X ^h	X ^h	X ^h		
Urine sample for urinalysis		X																																			X	X	X	

Procedure	Intervention period (Part B)																		Safety Follow-up ^b	Early discontinuation visit																	
	Day 350 ±7	Week 50	Day 364 ±7 ^a	Week 52	Day 378 ±7	Week 54	Day 392 ±7	Week 56	Day 406 ±7	Week 58	Day 420 ±7	Week 60	Day 434 ±7	Week 62	Day 448 ±7	Week 64	Day 462 ±7	Week 66	Day 476 ±7	Week 68	Day 490 ±7	Week 70	Day 504 ±7	Week 72	Day 532 ±7	Week 76	Day 560 ±7	Week 80	Day 588 ±7	Week 84	Day 616 ±7	Week 88	Day 644 ±7	Week 92	Day 672 ±7/ EOT	Week 96 / EOT	
Visit	21	22	23	24	25	26	27	28	29	30	31	32	33	34	35	36	37	38	39																		
Urine pregnancy test (WOCBP only) ⁱ																																					
C-SSRS questionnaire ^j			X																													X					
AE review																																X					
SAE review																																X					
Efficacy																																					
EDSS																				X										X		X					
Timed 25-foot walk test (T25-FW) ^k																				X										X		X					
9-hole peg test (9-HPT) ^k																				X										X		X					
Brain MRI with and without Gd																														X		X					
Clinical outcome assessment																																					
MSIS-29v2 ^l																														X		X					
MSWS-1 ^l																														X		X					

Procedure	Intervention period (Part B)																		Safety Follow-up ^b	Early discontinuation visit
	Week 50	Week 52	Week 54	Week 56	Week 58	Week 60	Week 62	Week 64	Week 66	Week 68	Week 70	Week 72	Week 76	Week 80	Week 84	Week 88	Week 92	Week 96 / EOT		
Visit	21	22	23	24	25	26	27	28	29	30	31	32	33	34	35	36	37	38	39	
Pharmacodynamics/biomarkers																				
Blood samples for sNfL													X						X	

Abbreviations: 9-HPT = 9-Hole Peg Test; AE = adverse event; C-SSRS = Columbia Suicide Severity Rating Scale; ECG = electrocardiogram; EDSS = Expanded Disability Status Scale; EOT = end of treatment; Gd = gadolinium; IMP = investigational medicinal product; IRT = interactive response technology; MRI = magnetic resonance imaging; MSIS-29v2 = Multiple Sclerosis Impact Scale-29 items version 2; MSWS-12 = multiple sclerosis walking scale 12 items; SAE = serious adverse event; sNfL = serum neurofilament light chain; T25-FW = Timed 25 foot walk test; WOCBP = woman of childbearing potential

- a The first visit for Part B is the Week 48 Visit in Part A. First dose of open-label (Part B) IMP will be taken at that visit, upon completion of all Week 48 assessments.
- b The participants will attend a safety follow-up visit within 2 weeks following discontinuation of IMP, if they no longer wish to remain in the study
- c In addition to the IMP being dispensed in the clinic, the IMP may be dispensed for home administration via direct-to-patient services, except if prohibited by local regulatory authorities during the intervening 3 months between site visits.
- d Only IMP reconciliation will be performed at this visit if participants are still on study intervention.
- e A brief physical examination will be performed at each visit.
- f A brief neurological examination including to cranial nerves, coordination/cerebellar function, reflexes, motor function, stance/gait will be performed at all visits.
- g Vital signs include blood pressure, heart rate, respiratory rate, and temperature. Refer to [Section 8.2.3](#) for further details.
- h Only laboratory tests for liver chemistry will be conducted: every two weeks (biweekly) from Week 50 through Week 72, every month from Week 72 through Week 96. Hence the only hematology and chemistry laboratory tests performed at the visits denoted with the footnote "h" are liver chemistry assessments. On-site, local laboratory or home health nurse, are permitted based on availability. These can be conducted remotely. In such cases, the blood sample must be collected at a local clinic or at home by a nurse, and the sample must be tested at a local lab or the central lab. In case of testing at a local lab, the study site staff must contact participants, within 2 working days after the results are expected to be available, to collect results of blood test. The following parameters will be investigated: alkaline phosphatase (ALP), alanine transaminase (ALT), aspartate aminotransferase (AST), gamma-glutamyl transferase (GGT), and bilirubin.
- i A urine pregnancy test will be provided direct-to-patient on a monthly basis except for the months coinciding with scheduled clinic visits (Weeks 52, 72, and 96).
- j The "Since Last Visit" version of the C-SSRS will be used.
- k 9-HPT: All individuals will complete a practice test and an actual test for both hands (1 task [right and left hand]). T25FW: the amount of time will vary for each participant.
- l MSIS-29v2 and MSWS-12 will be completed by participants prior to discussion of health status or other tests, and prior to administration of IMP. MSIS-29v2 will be self-administered, with a recall/observation period of 2 weeks. The time to complete MSIS-29v2 is 2 to 4 minutes. MSWS-12 will be self-administered with a recall/observation period of 2 weeks. The time to complete MSWS-12 is less than 5 minutes.

2 INTRODUCTION

SAR443820 is a novel, potent, selective, CNS-penetrant RIPK1 inhibitor that is being developed for neurodegenerative diseases, including MS.

2.1 STUDY RATIONALE

Multiple sclerosis is a chronic autoimmune disease characterized by neuroinflammation, demyelination, and axonal degeneration (1). Despite the availability of several DMTs that reduce relapses, there is still a significant unmet need for therapies that target disease progression in relapsing and progressive forms of MS (2). Clinically, most relapsing signs are effectively controlled with a broad arsenal of DMTs that target the peripheral adaptive immune system. Even when the relapses are well-controlled, ongoing inflammatory activity in the CNS inflicts insidious chronic damage and progressive physical disability predominates in absence of relapse activity (3, 4). This is particularly true for people with progressive forms of MS including PPMS and SPMS leading to relentless accumulation of nervous system disability. This is in part due to a complex cellular and biochemical milieu that perpetuates mediators of inflammation, leading to neuroaxonal damage and demyelination (3, 4).

Receptor interacting serine/threonine-protein kinase is a critical signaling protein in the TNFR1 pathway that regulates inflammation and cell death in tissues throughout the body. RIPK1 is activated in response to several inflammatory stimuli, with subsequent initiation of a complex signaling cascade that triggers intracellular responses, including cytokine release, microglial activation, and necroptosis, a regulated form of cell death. There is evidence for RIPK1, RIPK3, and MLKL activation in MS postmortem tissue, playing a role in both microglial and astrocyte inflammatory signaling and necroptosis of oligodendrocytes, which can be subject to RIPK1-dependent cell death. Inhibition of RIPK1 activity has been shown to protect against necroptotic cell death in vitro across a range of cell death models (5, 6, 7). Genetic and pharmacological inhibition of RIPK1 kinase ameliorated disease pathology and disease scores, improved animal behavior, attenuated the production of proinflammatory cytokines, reduced plasma neurofilament heavy chain levels, and decreased recruitment of immune cells in 2 animal models of MS, the EAE, and cuprizone models (5, 7), recapitulating certain aspects of immunological and degenerative components of MS (3, 4). These nonclinical findings coupled with observations of increased RIPK1 activity in human disease suggest a CNS-penetrant RIPK1 inhibitor may be beneficial in treating neurological diseases such as MS (5, 6, 7).

SAR443820 is a selective, orally bioavailable, CNS-penetrant, reversible kinase inhibitor of RIPK1. SAR443820 has demonstrated strong RIPK1 inhibition with high potency in vitro in various cell types. Dose ranging from 10 mg to 40 mg daily and 15 mg to 20 mg BID were safe and well tolerated. The FIH SAD (Study TDU16519) and MAD (Study TDR16520) showed a good tolerability and PK profile ($t_{1/2}$ 7 to 9 hours and t_{max} 1 to 2 hours), a strong target engagement relative to the RIPK1 inhibition evidenced at peripheral level and good penetration of SAR443820 in CSF.

Neuronal loss is a hallmark pathological feature of MS that is associated with brain atrophy, disease progression, and long-term disability (7, 8, 9). Neurofilaments (heavy and light chains) are structural elements of axons and markers of neuronal damage. Neurofilaments are increased in the CSF, plasma, and serum in a range of neurological diseases including MS (10). Neurofilament light chain levels have been demonstrated in numerous studies to be predictive of disease course and are responsive to DMTs in MS (11). Most approved and clinically effective MS treatments also reduce sNfL levels serving as a surrogate biomarker of treatment efficacy in numerous RRMS, PPMS, and SPMS randomized clinical trials (12, 13, 14). Therapeutic administration of a CNS-penetrant RIPK1 inhibitor has been demonstrated to cause dose-dependent reduction in disease score and plasma heavy chain neurofilament in the EAE animal model, substantiating neurofilament's suitability for objectively measuring SAR443820's effect on this marker in MS patients while evaluating the clinical and radiological signs that may respond to this intervention, especially the degenerative aspects that axonal injury manifests in the form of neurofilament elevation across the spectrum of neurological disease (7, 10, 11).

The aim of the ACT16753 Phase 2 proof-of-concept is to demonstrate SAR443820's effects on sNfL levels when compared to placebo in RRMS, SPMS, and PPMS participants. This study will also evaluate the effect of SAR443820 on clinical and imaging markers of disease progression and activity. Participants will be permitted to continue specified SOC background therapies (see [Section 5](#)) throughout the double-blinded treatment (Part A) and open-label long-term extension period (Part B). Safety and tolerability of SAR443820 will be monitored throughout the trial.

2.2 BACKGROUND

Immunomodulatory drugs have been the mainstay of MS therapy, most of which target the peripheral immune response, and have conferred significant benefit to patients suffering from MS with clinical relapses and MRI activity.

There is still a significant unmet need for therapies that target neuroinflammation in the CNS with the goal of halting long-term disability and neurodegeneration in all diagnostic categories of MS (ie, progressive forms of the disease such as PPMS and SPMS, as well as progression in RRMS) (15). Even the most recent high efficacy DMTs act mainly on adaptive immunity in the periphery with only modest or temporary ability to slow neuroinflammatory and neurodegenerative processes and stop disease progression (10, 11). Therefore, development of MS treatments with new modes of action is of interest.

Beyond the existing strategy to modulate cellular elements of adaptive immunity, there is mounting evidence that innate immunity, mediated by cells of a myeloid lineage (eg, bone marrow-derived monocytes, macrophages, and CNS resident microglial cells), is responsible for many of the neurodegenerative aspects of MS that persist in spite of the effectiveness of approved DMTs in preventing acute relapses (11, 15). Modulation of innate immunity has the potential to curtail such neuroinflammation and other manifestations of disease progression that remain unaddressed by current, approved therapies.

SAR443820 has demonstrated strong RIPK1 inhibition with high potency in vitro in various cell types and has been investigated in 4 clinical trials. Overall, in 100 healthy participants, doses

ranging from 10 mg to 40 mg daily and 15 to 20 mg BID were safe and well tolerated. The FIH SAD (Study TDU16519) and MAD (Study TDR16520) studies showed a good tolerability and PK profile ($t_{1/2}$ of 7 to 9 hours and t_{max} of 1 to 2 hours), strong target engagement relative to the RIPK1 inhibition evidenced at the peripheral level, and good penetration of SAR443820 in CSF. A preliminary PK-PD model has been developed using PD data [REDACTED]

[REDACTED] from the SAD and MAD. Typical I_{max} and IC_{50} values were [REDACTED] % and [REDACTED] ng/mL, respectively, confirming the [REDACTED] efficacy and potency of SAR443820 on pRIPK1 inhibition. Study BDR16957 evaluated the relative bioavailability between tablet and capsule formulations in Part 1 and showed [REDACTED] of the SAR443820 formulation, and in Part 2, [REDACTED] of SAR443820 administered in fasted or fed (high-fat meal) conditions were observed. Study PKM17247 assessed safety and PK in East Asian healthy participants (Chinese and Japanese cohorts). [REDACTED]. Refer to the SAR443820 Investigator's Brochure (IB) for detailed descriptions of the chemistry, pharmacology, efficacy, and safety of SAR443820.

2.3 BENEFIT/RISK ASSESSMENT

2.3.1 Risk assessment

Table 1 - Risk assessment (identified risk of clinical significance)

Identified risk of clinical significance	Summary of data/rationale for risk	Mitigation strategy
Study intervention(s)		
Drug induced liver injury (DILI)	During clinical trials with SAR443820, mild-severe ALT increases have been reported, including 2 SUSARs with total bilirubin increase >2 ULN (DILI) reported in the ALS patients. These events often involved patients who were also taking concomitant medications that are known to induce liver function abnormalities, or who had concomitant diseases that could also affect ALT level. A lower percentage of ALT increases greater than $3 \times$ ULN have been reported in the ongoing phase 2 MS study (ACT16753)	Hepatic impairment will be considered by excluding participants with moderate to severe hepatic impairment (see item 5 of Section 2.3.3). All participants are requested to undergo biweekly liver chemistry monitoring from D1 through Week 24, then monthly liver chemistry monitoring from Week 28 through Week 48. In Part B all participants are requested to undergo biweekly liver chemistry monitoring from Week 50 through Week 72, and then monthly liver chemistry monitoring through Week 96. Participants will be discontinued from the study based on ALT levels. Detailed instructions to be followed in case of the occurrence of an AESI of ALT increase >3 ULN are described in Appendix 6 in this protocol, and cover ALT monitoring, IMP administration, etiology assessment and IMP rechallenge

Abbreviations: ALT = alanine transaminase; DILI = drug induced liver injury; IMP = investigational medicinal product.

Table 2 - Risk assessment (potential risk of clinical significance)

Potential risk of clinical significance	Summary of data/rationale for risk	Mitigation strategy
Study intervention(s)		
Convulsion/seizures	
Convulsions are considered a potential risk based on nonclinical findings in single-dose, 10 and 28-day nonhuman primate toxicity studies and in a 6-month rat study.
 
In nonhuman primate studies, convulsions/tremors were observed at 75 mg/kg in the single-dose study, at 100 mg/kg/day in the 10-day study, and at 60 mg/kg/day in the 28-day study.
 
No convulsions were observed in the 3 or 9-month monkey studies at dose levels up to █ mg/kg/day (the highest dose tested in these studies).
 
In an in vivo genetic toxicity study in rats, convulsions were observed after a single dose of 500 mg/kg and above. In the 6- and 9-month studies in rats, convulsions were noted at 400 mg/kg/day (males) and 200 mg/kg/day (females). Convulsions and other findings that necessitated euthanasia were also observed in a single female rat receiving 50 mg/kg/day.
	
Based on the uncertainty in the interspecies translatability of convulsive risk, a conservative safety approach to limit human exposure (ie, C_{max} and AUC) was taken regarding the selected dose of 20 mg QD, which maintained a minimum of a █ to the NOAEL exposure (C_{max} and AUC) in the 6-month toxicology study in rat and 9-month toxicology study in nonhuman primate.
 
Excluding participants in whom exposure may be increased (participants weighing <45 kg, or participant with moderate or severe hepatic impairment).
 
Moreover, to mitigate risk, participants with a history of noninfantile seizure will not be eligible to participate in this study.
 
Additionally, concomitant medications that may increase the risk of seizure or increase exposure (moderate or strong cytochrome P450 [CYP]3A4 inhibitors or strong inducers of CYP3A4) are not allowed in the study.
 
Convulsion will be considered an AESI.

Immunomodulatory effects	Findings consistent with immune system modulation were observed with SAR443820 in the 3- and 9-month nonhuman primate studies. These pathological findings included mononuclear cell infiltrates in various tissues and changes in lymphoid tissues (increased/decreased cellularity and/or increased germinal centers). None of these microscopic findings for SAR443820 were considered adverse based on incidence, severity, and/or recoverability, as well as the lack of clinical pathology correlates or relevant clinical observations.	
Frequent monitoring via hematology tests, physical examinations (eg, skin, lymph nodes), and occurrence of infection TEAEs is planned.
 
Serious infection will be considered an AESI.

Off target potential risks		
Thrombocytopenia	Related to other similar compounds, and to a potential bone marrow effect	Regular CBC assessments will be performed.
Anemia		
Skin reaction		Clinical examination will be performed.
Study procedures		
Blood drawing	Pain or other discomfort from collection of blood samples	Minimize the frequency and amount of blood drawing.

Abbreviations: AESI = adverse event of special interest; ALT = alanine aminotransferase; AUC = area under the curve; CBC = complete blood count; C_{max} = maximum plasma concentration; NOAEL = no-observable-adverse-effect level; Pop PK = population pharmacokinetic; QD: once daily; TEAEs = treatment-emergent adverse events

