2.3.3 Overall benefit/risk conclusion

In the completed FIH studies, SAR443820 was safe and well-tolerated up to the highest doses administered, ie, a single dose of [REDACTED] mg and 14-day dose of 20 mg BID in healthy volunteers who received SAR443820 as of November 2021. Neither convulsions, immunomodulatory effects, thrombocytopenia, anemia, skin reactions, nor infections were observed. In addition, a preliminary physiologically based pharmacokinetic (PBPK) model indicates that at the dose of 20 mg QD, [REDACTED] (RIPK1 auto-phosphorylation inhibition test [pSer166-RIPK1] in peripheral blood mononuclear cell [PBMC] lysates) during the dosing interval. Convulsions believed to be SAR443820 related have been observed in [REDACTED] at similar SAR443820 levels in plasma. The risk of convulsion will be mitigated through the following:

1. limiting the dose chosen in this study with maximum plasma concentration (C_{max}) and area under the curve (AUC) that are [REDACTED] at the no-observed-adverse-effect level (NOAEL) in the [REDACTED] studies;
2. excluding participants with a history of seizures;
3. excluding concomitant medications that may increase the risk of seizures;
4. excluding concomitant medications that may increase exposure (moderate or strong CYP3A4 inhibitors);
5. excluding participants with moderate or severe hepatic impairment and with body weight <45 kg.

In the ongoing study ACT16970, a limited number of cases meeting criteria for severe DILI have been reported. ALT and bilirubin levels fully recovered in these cases after stopping the IMP and riluzole. These blinded data suggest that DILI is an identified risk of SAR443820, in particular when used in combination with hepatotoxic concomitant medications. The exact mechanism is not known. In nonclinical studies in rats and monkeys, non-adverse microscopic changes were noted in the liver without ALT increases. In Phase 1 studies, there were three mild (<3 ULN) asymptomatic cases of ALT increase (all recovered). Risk minimization measures during the study include limitation of alcohol consumption, although a relationship with alcohol use has not been established.

In addition, frequent monitoring of safety through hematology and liver chemistry tests, physical examination (eg, skin, lymph nodes), and occurrence of infections, will be implemented in both Parts A and B.

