7.1 DISCONTINUATION OF STUDY INTERVENTION

7.1.1 Permanent discontinuation

Compliance with and continuation of the study intervention is encouraged, while maintaining the safety of study participants and integrity of the study. In certain instances, it may be medically necessary for a participant to permanently discontinue study intervention.

In case of the events listed below, permanent discontinuation of the IMP is mandatory (this list is not intended to be exclusive):

- The Investigator or Sponsor determines it is in the best interest of the participant.
- Occurrence of AEs or any other medical condition that, in the opinion of the Investigator or Sponsor, may jeopardize the participant's safety or data integrity. These include, but are not limited to, abnormal livers tests and meeting the stopping criteria.
- Noncompliance with the protocol, dosing regimen and visits including switching DMT or taking a prohibited DMT in Part A or Part B.
- Pregnancy of a female participant.
- Occurrence of convulsions.

Any abnormal laboratory value or ECG parameter will be immediately rechecked for confirmation after 24 hours before making a decision regarding permanent discontinuation of the IMP for the concerned participant.

Handling of participants after permanent intervention discontinuation

If a participant is withdrawn from study intervention permanently, the Sponsor will be notified within 2 business days and the date and reason(s) for the withdrawal will be documented by the Investigator in the appropriate pages of the eCRF when considered as confirmed.

Participants will be followed up according to the study procedures specified in this protocol up to study completion, or up to recovery or stabilization of any AE to be followed up as specified in this protocol, whichever comes last.

If possible, and after the definitive discontinuation of intervention, the participants will be assessed using the procedure normally planned for the last treatment day with the IMP including a PK sample. Details are provided in the SoA ([Section 1.3](#)). All cases of definitive intervention discontinuation must be recorded by the Investigator in the appropriate pages of the eCRF when considered as confirmed.

All cases of permanent intervention discontinuation must be recorded by the Investigator in the appropriate pages of the eCRF when considered as confirmed.

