7.1.2 Liver function stopping criteria

Discontinuation of study intervention for abnormal liver tests is required by the Investigator when a participant meets one of the conditions outlined in [Section 10.6](#) or in the presence of abnormal liver chemistry test results not meeting protocol-specified stopping rules if the Investigator believes that it is in best interest of the participant.

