7.2 PARTICIPANT DISCONTINUATION/WITHDRAWAL FROM THE STUDY

- A participant may withdraw from the study at any time at his/her own request or may be withdrawn at any time at the discretion of the Investigator for safety, behavioral or compliance reasons.
- At the time of discontinuing from the study, if possible, an early discontinuation visit should be conducted, as shown in the SoA. See the SoA for data to be collected at the time of study discontinuation and follow-up and for any further evaluations that need to be completed.
- If the participant withdraws consent for disclosure of future information, the Sponsor may retain and continue to use any data collected before such a withdrawal of consent.
- If a participant withdraws from the study, he/she may request destruction of any samples taken and not tested, and the Investigator must document this in the site study records.

For Part A and Part B, if a participant no longer wishes to take the IMP, they will be encouraged to remain in the study or to attend a safety follow-up visit within 2 weeks following discontinuation of IMP.

NOTE: No IMP reconciliation is expected at the “Safety Follow-up” visit.

The Investigators should discuss with them key visits to attend. The value of all their study data collected during their continued involvement will be emphasized as important to the public health value of the study.

Participants who withdraw from the study intervention should be explicitly asked about the contribution of possible AEs to their decision, and any AE information elicited must be documented.

All study withdrawals should be recorded by the Investigator in the appropriate screens of the eCRF and in the participant's medical records. In the medical record, at least the date of the withdrawal and the reason should be documented.

In addition, a participant may withdraw his/her consent to stop participating in the study. Withdrawal of consent for intervention should be distinguished from withdrawal of consent for follow-up visits and from withdrawal of consent for non-participant contact follow-up, eg, medical record checks. The site should document any case of withdrawal of consent.

Participants who have withdrawn from the study cannot be rerandomized/reallocated (treated) in the study. Their inclusion and intervention numbers must not be reused.

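### Protocol Table 1 ends study participation on ALT levels, while Section 7 ends only study intervention; the texts need reconciling to protect post-drug data outside the primary analysis

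*Protocol*

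**What the plan says.** Protocol 2.3.1, Table 1, deals with drug-induced liver injury, the one identified risk. Its mitigation text says: "Participants will be discontinued from the study based on ALT levels". The next sentence refers sites to Appendix 6 for instructions that "cover ALT monitoring, IMP administration, etiology assessment and IMP rechallenge".

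Section 7 handles liver abnormalities differently:

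- Section 7.1.2: "Discontinuation of study intervention for abnormal liver tests is required by the Investigator when a participant meets one of the conditions outlined in" Section 10.6 (Appendix 6). It also allows the drug to be stopped on the Investigator's judgment when those conditions are not met.
- Section 7.1.1 lists abnormal liver tests among the grounds for permanent discontinuation of the drug, and then says: "Participants will be followed up according to the study procedures specified in this protocol up to study completion", or until any adverse event under follow-up has recovered or stabilized, whichever is later.
- Section 7.1.4.1 rules out rechallenge in confirmed liver injury caused by the drug and requires permanent discontinuation of the drug, not of the study.
- Section 7.2 covers leaving the study. A participant "may be withdrawn at any time at the discretion of the Investigator for safety, behavioral or compliance reasons", but no ALT trigger is given. It adds: "Participants who have withdrawn from the study cannot be rerandomized/reallocated (treated) in the study".

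Protocol 4.1 and SAP 1.1 send participants who stop treatment to an early discontinuation visit up to 2 weeks after the last dose, and do not say there whether scheduled visits continue afterwards.

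**The concern.** A site applying Table 1 literally would end participation when an ALT rule is met. A site applying Section 7 would stop the drug and keep the participant on the visit schedule. These are different data sets from the same event.

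The SAP relies on stopping the drug and leaving the study being separate things. SAP 3.2.4 uses sNfL collected after the drug stops and treats it as missing, under a missing-at-random assumption, once a participant leaves the study. SAP 3.3.2 and 3.4.2 include post-discontinuation measurements for all secondary and tertiary efficacy endpoints. The liver analyses in SAP 3.6.3.1 classify ALT elevations partly by whether they resolved after the last dose.

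Protocol 2.3.3 says: "These blinded data suggest that DILI is an identified risk of SAR443820". Exits triggered by ALT would therefore plausibly be more frequent in the SAR443820 arm during Part A, and the resulting missingness would be related to treatment. In Part B everyone receives SAR443820, so that contrast no longer applies in the same way.

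**Working it through.** The plan states no figure on this point, so the check is mainly a comparison of texts.

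1. **Same event, two outcomes.** Table 1 ends study participation on ALT levels. Sections 7.1.1, 7.1.2 and 7.1.4.1 end study intervention, and 7.1.1 continues follow-up. All of this is current body text, not a record of superseded wording.

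2. **Table 1 against its own next sentence.** Rechallenge requires a participant who is still in the study. Section 7.2 bars treating someone who has withdrawn. Study exit on ALT and later rechallenge cannot both apply to one participant.

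3. **Section 7.2 does not bridge the gap.** Withdrawal from the study for safety is at the Investigator's discretion. Table 1 reads as a rule.

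4. **Which analyses would lose data if Table 1 were followed.**
   - Primary sNfL analysis (SAP 3.2.2.1): none. It uses only assessments before drug discontinuation, so an ALT stop removes later samples under either wording.
   - Supplementary treatment-policy sNfL analysis (SAP 3.2.4): later samples become missing.
   - Secondary and tertiary efficacy endpoints (SAP 3.3.2, 3.4.2): later measurements are lost.
   - ALT recovery summary (SAP 3.6.3.1): later scheduled values are lost, so recovery after the last dose is less fully observed.

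5. **What liver follow-up would remain.** Section 8.2.5 requires clinically significant abnormal values to be repeated until they normalize, return to baseline or lose significance. Section 8.3.9 makes an ALT increase an event of special interest, and Section 8.3.3 has such events followed to resolution or stabilization. The triggering event is therefore still followed. What goes is the scheduled liver chemistry afterwards, and Section 8.3.1 removes any duty to seek adverse events actively once participation has ended.

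6. **Number of participants.** Protocol 4.1 gives 84 participants on SAR443820. No ALT-stop rate is given, so the rates here are assumptions. Participants affected = 84 × assumed rate:
   - 1%: 84 × 0.01 = 0.84, about 1
   - 3%: 84 × 0.03 = 2.52, about 3
   - 5%: 84 × 0.05 = 4.2, about 4
   - 10%: 84 × 0.10 = 8.4, about 8

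**The case against.** The best defence is that Table 1 is a benefit-risk summary and not the operative text. It passes sites straight to Appendix 6 for detail, and what it lists there includes drug administration and rechallenge, which presuppose continued participation. On that reading the sentence is loose wording for stopping the drug. This is plausible, and it lowers the chance that sites would act on Table 1. It does not remove the conflict: the sentence stands in current text for the main safety risk. The Appendix 6 ALT chart is not shown in the document available here, so it could not be checked.

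Three stronger readings are tempting, and the documents do not support them:

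- A reader might infer that ALT exits would use up part of the 17% dropout allowance (168 × 0.17 = 28.56, about 29 participants) and weaken the primary result. That allowance serves the precision of the primary geometric mean ratio. An ALT stop ends a participant's contribution to that analysis under either wording, so the loss cannot be attributed to Table 1.
- A reader might infer that exits would fall entirely in one arm. The data behind the risk statement are described as blinded, and Table 1 says the events often involved other medications or diseases that affect the liver. Some imbalance is plausible; complete imbalance is not shown.
- A reader might infer that liver follow-up would be lost altogether. Sections 8.2.5 and 8.3.3 keep the triggering event under follow-up.

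It is also fair to say that Section 7 does not guarantee complete post-drug data. Section 7.2 and SAP 3.2.4 encourage participants either to remain or to attend a safety visit within 2 weeks, and Protocol 4.1 and SAP 1.1 leave retention after a drug stop unclear. Correcting Table 1 alone would leave that ambiguity in place.

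**Conclusion.** The contradiction holds and is more than clerical, because it concerns the handling of the one identified risk and decides whether planned post-drug data exist for the participants affected. Its reach is limited to later scheduled liver chemistry, the supplementary treatment-policy sNfL analysis, the secondary and tertiary endpoints, and the ALT recovery summary. The primary hypothetical-strategy analysis is untouched.

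The documents do not allow the size to be stated. The range of about 1 to 8 SAR443820 participants rests wholly on an assumed 1% to 10% ALT-stop rate, and any loss further assumes that sites follow Table 1 rather than Section 7. The expectation of more exits on SAR443820 in Part A rests on the protocol's own classification of liver injury as an identified risk.

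**What to change.** Reconcile Table 1 in Protocol 2.3.1 with Sections 7.1.1, 7.1.2, 7.1.4.1 and 7.2, and with the early-discontinuation wording in Protocol 4.1 and SAP 1.1, so that one text states whether meeting the ALT rule ends study intervention or study participation. If it ends study intervention only, say that the scheduled sNfL, MRI, EDSS and liver visits continue, as Section 7.1.1 already provides. Which rule applies is for the sponsor to decide; no clinical rule or threshold is proposed here.

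The cost is about one sentence in Table 1 at the next protocol amendment, with matching wording in Protocol 4.1 and SAP 1.1. No analysis method or sample size changes.
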